Diarrhea: At the 2 mg monotherapy dose, 33% to 58% of patients in five trials had diarrhea (Investigator's Brochure, 2013). Of ~320 subjects (including crossover subjects) with diarrhea at this dose, the majority of diarrhea AEs were grade 1 or 2 in severity (33% to 56% of all study patients); 17 patients had grade 3 diarrhea, and none had grade 4 diarrhea.

Visual disorders: At the 2 mg monotherapy dose, 4% to 21% of the patients in five trials experienced visual disorders (Investigator's Brochure, 2013). Of the 85 total subjects (including crossover subjects) experiencing visual disorders at this dose level, the majority of visual disorders were grades 1 or 2 (4% to 20% of all study patients); six patients experienced grade 3 visual disorders, and one patient experienced a grade 4

visual disorder.

- Retinal Pigment Epithelial Detachment (RPED): Also known as chorioretinopathy, RPED is a visual impairment due to fluid accumulation under the retina and causes blurry vision. There were five cases of RPED, previously termed central serous retinopathy, reported from the integrated trametinib safety population consisting of subjects treated with trametinib 2 mg once daily from five studies (Investigator's Brochure, 2013). As of 23 June 2013, 14 cases of RPED were reported across the entire trametinib program amongst subjects treated with trametinib either as monotherapy or in combination with other anti-cancer agents (including cases from a MEK/BRAF combination study).
- Retinal vein occlusion (RVO): As of 23 June 2013, a total of four cases of RVO were reported across the entire trametinib program (including one case from a MEK/BRAF combination study) (Investigator's Brochure, 2013). All cases of RVO occurred in one eye only. Study drug was stopped at time of diagnosis in all cases. There was a decrease of visual acuity in two subjects with central RVO (CRVO) while the other two subjects had no meaningful decrease of visual acuity. In the two subjects with CRVO, local treatment with intravitreal injections of anti-VEGF antibodies was initiated within 2 weeks after RVO diagnosis, and visual acuity improved in one subject and restored to baseline conditions in another subject, at the time of the data cutoff. Three of these four cases were considered related to study treatment by the investigators.

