Hepatic disorders: Abnormalities of liver enzymes and bilirubin have been observed with administration of trametinib (Investigator's Brochure, 2013). However, assessment of these cases was often confounded by co-morbid conditions (such as biliary obstruction), concomitant use of other potentially hepatotoxic drugs, and liver metastases. At the 2 mg monotherapy dose, 8% to 34% of patients in five trials had LFT abnormalities. Of the 96 total patients (including crossovers) with LFT changes, the majority were grade 1 or 2 in severity (4% to 20% of all study patients); 26 had grade 3 events, and 6 patients had grade 4 events.

Cardiac-related AEs: At the 2 mg monotherapy dose, 3% to 21% of the subjects in six studies had cardiac-related AEs (Investigator's Brochure, 2013). Of the 65 total subjects (including crossover subjects) experiencing cardiac-related AEs at the 2.0 mg monotherapy dose in five of the studies, the majority of cardiac-related AEs were grades 1 or 2 in severity (0% to 16% of all study subjects); 18 subjects had grade 3 cardiac-related AEs, and no subjects had Grade 4 cardiac-related AEs in any study. No subject in one study, which evaluated the effect of repeat oral dosing of trametinib 2 mg QD on cardiac repolarization in subjects with solid tumors, had cardiac-related AEs. One study subject receiving trametinib 2 mg QD had grade 5 (fatal) acute cardiac failure, with evidence of massive tumor invasion of the heart; this AE was considered not drug-related by the investigator.

In the phase 3 trial of trametinib vs. chemotherapy in patients with melanoma (MEK114267), cardiomyopathy (defined as cardiac failure, left ventricular dysfunction, or decreased LVEF) occurred in 7% (14/211) of patients treated with trametinib, and in no patients in the chemotherapy arm. Cardiomyopathy was identified within the first month of treatment in five of these 14 patients; median onset of cardiomyopathy was 63 days (range: 16 to 156 days). Cardiomyopathy resolved in 10 of these 14 (71%) patients. Cardiac monitoring should be included in trametinib protocols, to include LVEF assessment by echocardiogram or MUGA scan at baseline, one month after initiation of trametinib and then at 2- to 3-month intervals while on treatment. Refer to dose modification guidelines for cardiac AEs in the event of LVEF decline or symptomatic cardiac AEs.

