5.2 Definition of Dose-Limiting Toxicity

Dose-limiting toxicity (DLT) is based on the CTEP Active Version 4 of the NCI Common Terminology Criteria for Adverse Events (CTCAE). CTCAE v5.0 will be utilized beginning April 1, 2018. DLT refers to toxicities experienced during the first 42 days of treatment. A DLT will be defined as follows:

Any grade 4 toxicity

Version Date: July 22, 2022

- Grade 3 fatigue, persistent for more than 7 days
- Grade ≥ 3 nausea, diarrhea, or vomiting despite maximum supportive care and persisting more than 72 hours
- Grade \geq 3 neutropenia with fever > 38.5°C
- Grade 3 thrombocytopenia with clinically significant bleeding. Clinically significant bleeding will be defined as any bleeding requiring transfusion, hospitalization, or medical or surgical intervention. Clinically significant bleeding will only be considered a DLT if it is associated and attributable to study drug induced thrombocytopenia.
- Ejection fraction < lower limit of normal (LLN) with an absolute decrease of >10% from baseline with confirming assessment within 7 days.

Management and dose modifications associated with the above adverse events are outlined in Section 6.

Dose escalation will proceed within each cohort according to the scheme shown in **Table 5.3** above. Dose-limiting toxicity (DLT) is defined above.

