6.1.3 Trametinib Dose Modifications for Visual Changes

Trametinib is known to be associated with visual adverse events. An ophthalmologist should be consulted if changes in vision develop. However, if the visual changes are clearly unrelated to study treatment (e.g., allergic conjunctivitis), then monitor closely as it may be reasonable to defer ophthalmic examination. Special attention should be given to retinal findings (e.g., retinal pigment epithelial detachment (RPED) or retinovascular abnormalities (i.e., branch or central retinal vein occlusions (RVO)). For events of visual changes (regardless of severity) for which an ophthalmic examination is conducted, a blood sample for PK analysis must be drawn as close as possible to the time of the event.

Patients are required to have a standard ophthalmic exam performed by an ophthalmologist at baseline and any time patients report visual disturbance. The exam will include best corrected visual acuity, tonometry slit lamp biomicroscopic examination, visual field examination, and indirect fundoscopy with special attention to retinal abnormalities. Optical coherence tomography is recommended at scheduled visits, and if retinal abnormalities are suspected. Other types of ancillary testing including color fundus photography and fluorescein angiography are also recommended if clinically indicated.

Guidelines regarding management and dose reduction for visual changes and/or ophthalmic examination findings considered to be related to study treatment are provided in the tables below.

Management and Dose Modification Guidelines for Visual Changes and/or Ophthalmic Examination Findings

CTCAE Grade ^a	Adverse Event Management	Action and Dose Modification
Grade 1 ^b	Consult ophthalmologist within 7	If dilated fundus examination cannot be performed within 7 days of onset, interrupt trametinib until RPED and RVO can be excluded by retina specialist/ophthalmologist.
		If RPED and RVO excluded, continue (or restart) trametinib at same dose level
		• If RPED suspected or diagnosed: see RPED dose modification table below (following this table); report as SAE.
		• If RVO diagnosed: Permanently discontinue trametinib and report as SAE.
C = 1 2 = 1	Consult ophthalmologist	Interrupt trametinib
Grade 2 and Grade 3	immediately	• If RPED and RVO excluded, restart trametinib at same dose level after visual AE is ≤ grade 1. If no recovery within 3 weeks, discontinue trametinib

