Criteria for discontinuing study drug: When any of the liver stopping criteria below is met, discontinue trametinib ALT ≥3xULN and bilirubin ≥2x ULN or >35% direct bilirubin 1,2 ALT ≥ 3xULN and INR >1.5, if INR measured² (INR threshold does not apply if subject is on anticoagulant) ALT ≥5x ULN ALT ≥3x ULN persists for ≥4 weeks ALT ≥3x ULN and cannot be monitored weekly for 4 weeks ALT ≥3x ULN associated with symptoms³ (new or worsening) believed to be related to liver injury or hypersensitivity	Immediately discontinue study treatment. Do not restart/rechallenge unless approved by CTEP trametinib medical monitor. Report as SAE if: 1) CTEP-AERS reporting criteria are met, or 2) patients meet criteria 1-2. Perform liver event ASSESSMENT AND WORKUP (see below). Monitor the subject until liver chemistries resolve, stabilize, or return to baseline (see MONITORING below). MONITORING: In patients stopping for criteria 1-2 (with abnormal TB and INR, indicating potentially more significant liver toxicities): Repeat liver chemistries (ALT, AST, ALK, bilirubin) and perform liver event follow-up assessments within 24 hours. Monitor subjects twice weekly until LFT return to normal/baseline or stabilize. A specialist or hepatology consultation is recommended. In patients stopping for criteria 3-6: Repeat LFT and perform liver event follow up assessments within 24-72 hrs Monitor subjects weekly until LFTs return to normal/baseline or stabilize. ASSESSMENT and WORKUP: Viral hepatitis serology. ⁴ If possible, obtain blood sample for PK analysis. ⁵ Serum CPK and LDH. Fractionate bilirubin, if total bilirubin ≥2x ULN. CBC with differential to assess eosinophilia. Record clinical symptoms of liver injury, or hypersensitivity on AE CRF. Record concomitant medications (including acetaminophen, herbal remedies, other over the counter medications). Record alcohol use. Additional work up for patient stopping for criteria 1-2 (with abnormal TB and INR, indicating potentially more significant
	liver toxicities): Anti-nuclear antibody, anti-smooth muscle antibody, Type 1 anti-liver kidney microsomal antibodies, and quantitative total

Version Date: July 22, 2022

Trametinib Dose Modification for Liver Function Test Abnormalities	
Event	Treatment modifications and assessment/monitoring
	immunoglobulin G (IgG or gamma globulins).
	Serum acetaminophen adduct HPLC assay (in subjects with
	likely acetaminophen use in the preceding).

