	If there is underlying chronic hepatitis B (e.g. positive hepatitis
	B surface antigen): quantitative hepatitis B DNA and hepatitis
	delta antibody. ⁶
	Liver imaging (ultrasound, MRI, CT) and /or liver biopsy.

Footnotes:

- 1. Serum bilirubin fractionation should be performed if testing is available. If serum bilirubin fractionation testing is unavailable, record presence of detectable urinary bilirubin on dipstick, which indicates direct bilirubin elevations and suggesting liver injury.
- 2. All events of ALT $\ge 3x$ ULN and bilirubin $\ge 2x$ ULN ($\ge 35\%$ direct bilirubin) or ALT $\ge 3x$ ULN and INR ≥ 1.5 (if INR measured) may indicate severe liver injury (possible "Hy's Law"). INR measurement is not required, and the threshold value stated will not apply to subjects receiving anticoagulants.
- 3. New or worsening symptoms believed to be related to liver injury (such as fatigue, nausea, vomiting, right upper quadrant pain or tenderness, or jaundice) or believed to be related to hypersensitivity (such as fever, rash or eosinophilia)
- 4. Includes: Hepatitis A IgM antibody; Hepatitis B surface antigen and Hepatitis B Core Antibody (IgM); Hepatitis C RNA; Cytomegalovirus IgM antibody; Epstein-Barr viral capsid antigen IgM antibody (or if unavailable, obtain heterophile antibody or monospot testing); Hepatitis E IgM antibody
- 5. PK sample is desired if feasible. Record the date/time of the PK blood sample draw and the date/time of the last dose of study treatment prior to blood sample draw on the CRF. If the date or time of the last dose is unclear, provide the subject's best approximation. If the date/time of the last dose cannot be approximated OR a PK sample cannot be collected in the time period indicated above, do not obtain a PK sample.
- 6. If hepatitis delta antibody assay cannot be performed, it can be replaced with a PCR of hepatitis D RNA virus (where needed) (Le Gal *et al.*, 2005).

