6.1.6 Trametinib Dose Modification for Pneumonitis

Pneumonitis has been observed in patients receiving trametinib. To reduce the risk of pneumonitis, patients will be monitored closely for symptoms and evaluated with imaging and functional tests. Dose modification and supportive care guidelines for pneumonitis are described in the tables below.

	Pneumonitis Guidelines for Trametinib Mon	otherapy
CTCAE Grade	Adverse Event Management	Action and Dose Modification
Grade 1	 CT scan (high-resolution with lung windows) recommended. Work-up for infection. Monitoring of oxygenation via pulse-oximetry recommended. Consultation with pulmonologist recommended. 	Continue trametinib at current dose.
Grade 2	 CT scan (high-resolution with lung windows). Work-up for infection. Consult pulmonologist. Pulmonary function tests: If < normal, repeat every 8 weeks until ≥ normal. Bronchoscopy with biopsy and/or BAL recommended. Symptomatic therapy including corticosteroids if clinically indicated. 	 Interrupt trametinib until recovery to grade ≤1. If AE resolved to grade ≤1 and relationship to trametinib is equivocal, restarting trametinib with one dose reduction may be considered, after discussion with the medical monitor. If treatment delay is > 4 weeks, permanently discontinue trametinib.
Grade 3	 CT scan (high-resolution with lung windows). Work-up for infection. Consult pulmonologist. Pulmonary function tests-if < normal, repeat every 8 weeks until ≥ normal. Bronchoscopy with biopsy and/or BAL if possible. Symptomatic therapy including corticosteroids as clinically indicated. 	 Interrupt trametinib until recovery to grade ≤1. If AE resolved to grade ≤1 and relationship to trametinib is equivocal, restarting trametinib with one dose reduction may be considered, after discussion with the medical monitor. If treatment delay is >4 weeks, permanently discontinue trametinib.
Grade 4	Same as grade 3.	Permanently discontinue trametinib.
Abbreviations: BA	L = bronchoalveolar lavage; CT = computed tomography	

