Asymptomatic SBP ≥160 mmHg, or DBP ≥100 mmHg, or Failure to achieve well-controlled BP within 2 weeks in Scenario A.	antihypertensive medication(s). • Titrate antihypertensive medication(s) during the next 2 weeks to achieve well-controlled BP.	indicated. • Once BP is well-controlled, restart trametinib reduced by one dose level. ^a
(Scenario C) ■ Symptomatic hypertension or Persistent SBP ≥160 mmHg, or DBP ≥100 mmHg, despite antihypertensive medication and dose reduction of study treatment	 Adjust current or initiate new antihypertensive medication(s). Titrate antihypertensive medication(s) during the next 2 weeks to achieve well-controlled BP. Referral to a specialist for further evaluation and follow-up is recommended. 	Interrupt trametinib. Once BP is well-controlled, restart trametinib reduced by one dose level.
(Scenario D) Refractory hypertension unresponsive to above interventions or hypertensive crisis.	Continue follow-up per protocol.	Permanently discontinue trametinib.
a: Escalation of trametinib to previous dose level can be considered if BPs remain well-controlled for 4 weeks after restarting of trametinib. Approval from the CTEP medical monitor is required.		

Management and Trametinib Dose Modification for Hypertension

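### The DLT list in Section 5.2 leaves out liver and retinal events below grade 4 that Section 6 requires trametinib to be stopped for at once, so the escalation and RP2D rules count those patients as DLT-free

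*Combined protocol and SAP*

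**What the plan says.** Section 5.2 sets the window and introduces a definition: "DLT refers to toxicities experienced during the first 42 days of treatment. A DLT will be defined as follows". The list has any grade 4 toxicity and five further items: prolonged grade 3 fatigue; persistent grade 3 or higher nausea, vomiting or diarrhea; grade 3 or higher neutropenia with fever; grade 3 thrombocytopenia with significant bleeding; and a confirmed fall in ejection fraction. There is no general grade 3 item and no item for a toxicity that ends treatment with one of the drugs.

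Table 5.3 and Section 5.1.1 use only that count. No DLT in three patients, or one in six, allows escalation. The RP2D is the highest level with at most one DLT in six.

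Section 6 requires trametinib to be stopped in situations that the list does not cover:

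- **Liver (6.1.5).** Stopping criteria include ALT at least 5x ULN; ALT at least 3x ULN with bilirubin at least 2x ULN or INR above 1.5; and ALT at least 3x ULN with symptoms. The action is immediate: "Do not restart/rechallenge unless approved by CTEP trametinib medical monitor". A footnote says that the combinations with raised bilirubin or INR "may indicate severe liver injury" and names Hy's Law.
- **Eye (6.1.3).** From grade 1 upward: "If RVO diagnosed: Permanently discontinue trametinib and report as SAE".

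Section 5.1.1 also lets investigators treat non-DLT toxicity as unacceptable. The stated consequence is a move to Schedule C. Formal safety reviews follow cohorts 3A and 3B.

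**The concern.** The Part 1 primary objective is to find the maximal doses at which both drugs can be given safely together. An event that ends one of the two drugs bears directly on that objective, yet it leaves the count unchanged. The opening of Section 6 says that when one drug is stopped the other continues. A patient taken off trametinib for possible Hy's Law injury can therefore complete the 42 days on navitoclax alone and be recorded as DLT-free. Alternatively the patient could be replaced, because Section 5.1.1 and Table 5.3 replace patients not evaluable for the DLT window without defining that term.

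The liver gap is the main one. Section 2.2.1.3 reports, for liver-test abnormalities at trametinib 2 mg, that "26 had grade 3 events, and 6 patients had grade 4 events". Most of the severe events therefore fell below the only grade at which 5.2 would count them. Liver toxicity is also shared: Section 2.2.2 says that enzyme elevations limited dosing in some navitoclax patients. In another trametinib combination, described in Section 2.2.1.5, grade 2 AST and ALT elevations were counted as DLTs.

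**Working it through.** **1. Is the event in the count?**

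| Event by day 42, below grade 4 | Section 6 action | On the 5.2 list? |
|---|---|---|
| ALT at least 5x ULN | Immediate stop | No |
| ALT at least 3x ULN with bilirubin at least 2x ULN or INR above 1.5 | Immediate stop | No |
| ALT at least 3x ULN with symptoms | Immediate stop | No |
| RVO, grades 1 to 3 | Permanent stop | No |
| Confirmed ejection fraction fall | Interrupt, possibly stop | Yes |
| Persistent grade 3 diarrhea | Interrupt, reduce dose | Yes |

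The liver criteria are written in multiples of ULN, not in CTCAE grades, and the protocol does not print the CTCAE cut-offs. I assume that criteria starting at 3x and 5x ULN can be met below grade 4. Of the grade 3 and 4 liver events quoted above, 26/(26 + 6) = 81% were grade 3. This is a split by grade, not a rate of meeting the stopping criteria.

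**2. Effect on one cohort.** Take six patients, one with a listed DLT and another stopped for ALT at least 3x ULN with bilirubin at least 2x ULN. As written the count is 1 of 6 and the level passes. With the second patient counted it is 2 of 6 and the level has exceeded the MTD.

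**3. The plan's own table.** For DLT probability p, the rule in Table 5.3 escalates with probability P(p) = (1−p)³ + 3p(1−p)²(1−p)³. For p = 10%, 20%, 30%, 40%, 50% and 60% this gives 90.6%, 70.9%, 49.4%, 30.9%, 17.2% and 8.2%. All six match the table in Section 13.1.1 (91, 71, 49, 31, 17 and 8%), so its arithmetic is right.

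**4. Size under an assumption.** Let d be the rate of listed DLTs and q the rate of patients whose only qualifying event is off-list. The documents do not give q; I assume 1% to 3%. As written p = d; with the events counted p = d + q. The six-patient rule passes with probability B(p) = (1−p)⁶ + 6p(1−p)⁵.

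| d | Quantity | As written | q = 1% | q = 3% | Overstatement (points) |
|---|---|---|---|---|---|
| 10% | P (escalate) | 90.6% | 88.9% | 85.3% | 1.7 to 5.3 |
| 20% | P (escalate) | 70.9% | 68.7% | 64.3% | 2.2 to 6.5 |
| 10% | B (at most 1 of 6) | 88.6% | 86.6% | 82.2% | 2.0 to 6.3 |
| 20% | B (at most 1 of 6) | 65.5% | 63.1% | 58.2% | 2.5 to 7.3 |

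Differences are taken before rounding. Example: P(0.13) = 0.87³ + 3(0.13)(0.87⁵) = 0.6585 + 0.1944 = 0.853.

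**5. Delayed stops.** A hold from day s to day 42 lasts 43 − s days. A hold of more than 21 days needs s ≤ 21, and one of more than 28 days needs s ≤ 14. Only early-starting delayed stops can fall within the window.

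**The case against.** **Existing discretion.** During Schedule A or B escalation, toxicity judged unacceptable has the same stated consequence as more than one DLT, and the last row of Table 5.3 gives the RP2D only as a general rule. This stands as mitigation. But the clause has no threshold, does not change the count, and states no step for a level already on Schedule C. The formal reviews are tied to 3A and 3B.

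**Part 2 re-examines safety** as a primary objective in 48 to 100 patients. True, but that comes after the dose is chosen, and Section 13.1.2 states no toxicity boundary.

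**The liver evidence is soft.** Section 2.2.1.3 says these events were often confounded. In the phase 3 melanoma trial, grade 3–4 ALT increases were 3% on trametinib and 3% on chemotherapy (AST 2% and 1%). This stands, and is a reason not to claim a large effect. RVO is rarer still: "a total of four cases of RVO were reported across the entire trametinib program", and patients with a history or risk of it are excluded.

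**All patients are evaluable for toxicity** under Sections 11.1.1 and 13.5.1. That does not define evaluability for the DLT window, which drives replacement.

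A reader might also infer stronger points that the documents do not support:

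- *Related grade 2–3 pneumonitis is an omitted immediate stop.* Section 6.1.6 says that if the event resolves and its "relationship to trametinib is equivocal, restarting trametinib with one dose reduction may be considered". It states no immediate permanent stop at these grades; that comes after a delay of more than 4 weeks.
- *Refractory hypertension is an important omission.* The stop applies to "Refractory hypertension unresponsive to above interventions or hypertensive crisis". Apart from a crisis, it is generally reached after successive two-week titration steps, so few cases would qualify by day 42.
- *Any 21-day trametinib hold forces a stop.* That sentence is in 6.1.1, for toxicities not specified elsewhere. Diarrhea has its own 21-day limit; rash, RPED and pneumonitis have 4-week limits.
- *The effect is large.* With q = 5%, escalation would fall from 90.6% to 81.4% (d = 10%) or from 70.9% to 60.0% (d = 20%), but nothing in the documents establishes a rate that high for stops triggered within 42 days.

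**Conclusion.** The point holds in a limited form. The 5.2 list is closed, and it omits events below grade 4 for which Section 6 requires an immediate trametinib stop, chiefly the liver criteria and also RVO. Those patients enter Table 5.3 and the RP2D rule as DLT-free unless someone uses an undefined discretion. That conclusion rests on the text and on the assumption that the liver criteria can be met below grade 4.

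The size is not known from the documents. The overstatement of about 2 to 7 points depends wholly on the assumed 1% to 3% rate, and would be smaller if the discretionary clause were used. A reader should not infer that the chosen RP2D is unsafe: the documents contain no Part 1 toxicity results. Nor should a reader infer that 5.2 misses every Section 6 stop, since grade 4 events are covered. The change is worth making because it is cheap and concerns serious events.

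**What to change.** Add to Section 5.2: any toxicity at least possibly related to study drug for which a Section 6 discontinuation criterion is actually met on or before day 42. This includes the liver stopping criteria and RVO, whether or not rechallenge is later approved. It excludes stops made only because weekly ALT monitoring is not possible.

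Key the item to the date the criterion is met, not to the onset of the toxicity. Otherwise an event starting on day 42 with a 4-week criterion would hold up the cohort decision until about day 70 (42 + 28). Delayed stops (4-week rash, RPED, pneumonitis or ALT persistence; 21-day holds under 6.1.1 or 6.2) then count only if reached by day 42.

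State in Section 5.1.1 and Table 5.3 that a patient stopped for such an event counts as a DLT and is not replaced.

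Section 5.1.1 ended Schedule A and B escalation with protocol Version 10, and the documents do not say whether Schedule C escalation is still open. Apply the wording to any that remains. Re-tabulate the completed Part 1 levels with these events counted, labelled as a sensitivity check on the RP2D because the definition would be set after the data.

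The cost is protocol wording and one table from existing data. Escalation may stop slightly earlier, some confounded liver events may be counted, and stops that mature after day 42 stay uncounted.
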